Potentially Associated Adverse Events (PAAE): Based on the reported potential risks of vitamin C, thiamine, and/or hydrocortisone, several important risks have been identified that could be associated with administration of one or all three drugs and have been labeled as "potentially associated adverse events" (PAAE). All PAAEs occurring following randomization through the initial hospital stay will be recorded on the AE page in the EDC portal. Identified PAAEs include but are not limited to nephrolithiasis, hemolysis, (refer to **Section 13.5 Table** for a detailed list).

Serious Adverse Event: A serious adverse event (SAE) is an AE that occurs during the study (ie, after randomization through to hospital discharge or day 30 follow-up [whichever occurs first]), that fulfills one or more of the following criteria:

- 1. Results in death (for the purposes of this trial, deaths will be captured as clinical outcomes and only recorded as an SAE if deemed related to the investigational product)
- 2. Is life-threatening (places the subject at immediate risk of death from the event as it occurred)
- 3. Results in inpatient hospitalization or prolongation of an existing hospitalization
- 4. Results in a persistent or significant disability/incapacity
- 5. Results in a congenital anomaly/birth defect; OR
- 6. Is an important and significant medical event. (Based upon appropriate medical judgment, may jeopardize the subject's health and may require medical or surgical intervention to prevent one of the other outcomes listed in this definition).

Serious and Unexpected Adverse Event

Serious Adverse Events (see above) that are **Unexpected** (i.e. not consistent with the natural history of the disease under study) and deemed to be definitely or possibly study-related will be reported in an expedited manner to the DSMB (see **Reporting Rules** below).

Relationship to Investigational Product

Determination of the relationships between AEs and administration of Investigational Product is a clinical decision based on all available information at the time of the completion of the EDC. Research relatedness will be evaluated according to the following definitions:

UNRELATED	The temporal relationship between treatment exposure and the adverse event is unreasonable or incompatible and/or adverse event is clearly due to extraneous causes (e.g., underlying disease, environment)

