UNLIKELY	 Must have both of the following 2 conditions, but may have reasonable or only tenuous temporal relationship to intervention: 1. Could readily have been produced by the subject's clinical state, or environmental or other interventions. 2. Does not follow known pattern of response to intervention.
REASONABLE POSSIBILITY	 Must have at least 2 of the following 3 conditions: 1. Has a reasonable temporal relationship to intervention. 2. Could not readily have been produced by the subject's clinical state or environmental or other interventions. 3. Follows a known pattern of response to intervention.
DEFINITE	 Must have all 3 of the following conditions: 1. Has a reasonable temporal relationship to intervention. 2. Could not possibly have been produced by the subject's clinical state or have been due to environmental or other interventions. 3. Follows a known pattern of response to intervention.

Adverse Event Reporting Rules

All research-related AEs, PAAEs and SAEs will be submitted electronically through the EDC.

A. Timing of reporting and duration of tracking:

AE reporting: All research-related non-serious AEs will be recorded up to the first 5 days after enrollment (up to 4 days of drug infusion and 1-day post infusion) and will be reported on the AE page of the EDC, and will be summarized at quarterly intervals for DSMB review and summarized and reported for the annual IRB continual renewal.

PAAE reporting: All non-serious PAAEs occurring following randomization through the acute hospital stay will be reported on the AE page of the EDC, and will be summarized at quarterly intervals for DSMB review and summarized and reported for the annual IRB continual renewal. PAAEs deemed to be serious will be reported as per the SAE reporting process below.

SAE reporting: All SAEs occurring following randomization through the acute hospital stay or 30-days after enrollment, whichever comes first, that are unexpected and deemed to be study related will be

reported by the Investigator or designee to the DCC by entering the event on the AE page of the EDC without delay.

These events (both PAAEs and SAE) will be followed (by the site PI) for outcome until resolution/stabilization or until 30 days from enrollment whichever comes first.

B. Reporting Procedures

i. General Reporting Guideline:

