13.2. Institutional Review Board

The Johns Hopkins Medicine IRB will act as the single IRB of record (SIRB) for the VICTAS protocol. JHM IRB will initiate reliance agreements with each participating site (and any affiliate, where necessary) through the SMART IRB mechanism. All sites will be responsible for conducting a local context review, to ensure that the protocol is appropriate and reasonable for their respective study populations, however the JHM SIRB approval will serve as the IRB approval of record for the entire study. JHM IRB will

provide a letter of support from JHM IRB to serve as SIRB, a templated letter of support for relying sites to complete, a draft protocol to be adapted for local context, FWA instructions for participating sites, as applicable, and, SMART IRB instructions for participating sites.

The protocol and consent form will be reviewed and approved by the SIRB at Johns Hopkins University, School of Medicine and each participating center will perform a local context review prior to study initiation. Serious adverse experiences regardless of causality will be reported to the SIRB in accordance with the standard operating procedures and policies of the SIRB, and the study team will keep the SIRB informed as to the progress of the study. Any documents that the SIRB may need to fulfill its responsibilities (such as protocol, protocol amendments, Investigator's Brochure, consent forms, information concerning patient recruitment, payment or compensation procedures, or other pertinent information) will be submitted to the SIRB. The SIRB written unconditional approval of the study is initiated. No study materials or supplies will be shipped to any participating site until SIRB approval of that site has been secured. The IRB unconditional approval statement will be transmitted by the clinical coordinating center to each site investigator prior to the shipment of study supplies to the site. This approval must refer to the study by exact protocol title and number and should identify the documents reviewed and the date of review.

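### Section 10.6 contradicts itself on entering serious PAAEs and SAEs, so capture could vary by site and the by-arm safety tables could miss severe cases

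*Combined protocol and SAP*

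**What the plan says.** Section 10.6 covers these events in four places, and 13.2 adds a fifth.

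- **10.6, PAAE definition.** "All PAAEs occurring following randomization through the initial hospital stay will be recorded on the AE page in the EDC portal". No condition is set on seriousness, cause or expectedness. Section 13.5 names four PAAEs (nephrolithiasis, hemolysis, hypersensitivity reactions, injection site reactions) and refers back to 10.6 for how they are recorded.
- **10.6, Reporting Rules, opening line.** "All research-related AEs, PAAEs and SAEs will be submitted electronically through the EDC".
- **10.6 A, timing rules.** The AE rule covers research-related non-serious events in the first 5 days. The PAAE rule says "All non-serious PAAEs occurring following randomization through the acute hospital stay will be reported on the AE page of the EDC" and then "PAAEs deemed to be serious will be reported as per the SAE reporting process below". The SAE rule runs from randomization to the earlier of discharge and day 30 and takes only events that are "unexpected and deemed to be study related"; the site makes that report by entering the event promptly on the same AE page.
- **10.6 B.i.** The site must enter AEs and SAEs, with no filter stated. The 72-hour limit applies to SAEs that meet criteria.
- **13.2.** "Serious adverse experiences regardless of causality will be reported to the SIRB", in line with that board's own procedures.

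Two definitions in 10.6 matter here. Unexpected means "not consistent with the natural history of the disease under study". An event on the expected list still counts as study related if the investigator attributes it to the product or if it leads to discontinuation of the product. Section 11.4.4 then gives counts and percentages of AEs and SAEs by arm, without formal testing.

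**The concern.** Read on its own, part A asks for less as the event gets worse. A mild case of a named risk is entered on the PAAE rule. A serious case of the same risk must pass two judgements, on expectedness and relatedness, before entry is required. That pair of conditions is normally a trigger for expedited reporting. Here it also sits in the sentence that tells sites which serious events go into the database.

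The tables in 11.4.4 can show only what was entered. If sites differ in which sentence of 10.6 they follow, the serious end of the named risks is ascertained unevenly, and those tables become hard to interpret. The undertaking in 13.2 to report serious events whatever their cause also depends on sites having passed them on.

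**Working it through.** No arithmetic applies: the documents give no PAAE rate or expected count. The check is to follow each kind of event through each rule.

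| Event | PAAE definition | 10.6 A timing rules | Opening line of the rules | 10.6 B.i |
|---|---|---|---|---|
| Non-serious PAAE, judged unrelated | Recorded | Entered, acute stay | Unclear | Entered |
| Serious PAAE, unexpected and judged related | Recorded | Entered, to discharge or day 30 | Submitted | Entered |
| Serious PAAE, judged unrelated | Recorded | Entry not required | Unclear | Entered |
| Serious non-PAAE, related but expected | Not applicable | Fits neither the AE nor the SAE rule | Submitted | Entered |
| Serious expected non-PAAE that led to stopping study drug | Not applicable | Fits neither the AE nor the SAE rule | Submitted, since 10.6 then counts it as study related | Entered |

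The opening line is marked unclear because its qualifier, research-related, may govern AEs only or all three terms.

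**Third row.** The PAAE definition and B.i require entry; part A does not. The event is missing only where a site works from part A alone. That is a plausible way to work, because part A is the specific rule and its filter is underlined in the text.

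**Fourth and fifth rows.** The AE rule takes only non-serious events and the SAE rule only unexpected ones. A serious event that is expected falls between them even when 10.6 itself classes it as study related. Only the opening line and B.i catch it.

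**Which half of the filter matters for PAAEs.** Unexpected is measured against the natural history of the disease, not against the known effects of the drugs. Most of the four named risks would probably pass, so relatedness would do most of the filtering.

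**An example.** Take hemolysis in a patient with DIC. Section 10.6 lists anemia and DIC among expected events. Section 3.5 says acute hemolysis with high-dose vitamin C is known only in G6PD deficiency, and known deficiency is an exclusion. An investigator could therefore rate the event unlikely to be related: the clinical state could readily explain it, and it does not fit the known pattern. If it is non-serious, part A has it entered. If it is serious, part A does not require entry.

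**Windows.** Non-serious PAAEs run through the acute stay. The SAE rule stops at discharge or day 30, whichever is first.

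**The case against.** The strongest reply is that the recording rule is the PAAE definition, which is unconditional, and that part A concerns reporting. It sits under a heading on timing, asks for prompt entry, and uses the same two criteria that 10.6 elsewhere attaches to expedited DSMB review. On that reading the plan already separates recording from urgent reporting. B.i supports it. So does B.ii, which keeps SAEs downgraded by the DCC in aggregate review, and B.iii, which sends PAAEs and SAEs to the SIRB.

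Much of this stands, and it rules out several stronger readings that a reader might infer:

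- That the plan has a settled rule removing serious PAAEs, so that none judged unrelated or expected are captured while all non-serious ones are. This follows only if part A is read alone. Even the non-serious side is uncertain, given the qualifier in the opening line.
- That sites are told not to enter such events. No sentence forbids it; part A only fails to require it.
- That an excess of serious PAAEs in one arm could not be seen. Two other sentences in 10.6 require entry, and 11.4.4 tabulates both AEs and SAEs.
- That a serious PAAE after day 30 in a patient still in hospital is lost. The SAE definition itself ends at discharge or day 30, so the event is not a protocol SAE, and the PAAE definition still records it.

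The relatedness scale is also more inclusive than the hemolysis example suggests. Reasonable timing plus a known pattern of response is enough for a reasonable possibility, even where sepsis could explain the event.

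The reply does not remove the conflict. The SAE rule says the report is made by an entry on the AE page, which is the same act the PAAE definition requires for every PAAE. Separating recorded from reported therefore does not reconcile the two. Nor does the PAAE definition help with related-but-expected serious events that are not PAAEs.

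**Conclusion.** The point holds as an internal contradiction that leaves capture of serious PAAEs, and of related or discontinuation-causing serious events that count as expected, open to interpretation. Its consequence is conditional: sites that follow part A alone could leave such events out, sites that follow the general sentences would not, and the by-arm tables in 11.4.4 could then miss the most severe cases of the named risks.

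The number of events affected is unknown. It depends on how often these events occur, how investigators rate relatedness, and how many sites work from part A alone, and the documents give none of these. The reporting diagram announced in 10.6 is not shown and may clarify the routing; even so, the written rules would still need to agree with each other. The point merits correction because it concerns ascertainment of the risks the plan itself names, and the remedy is small.

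**What to change.** Reconcile the PAAE definition, parts A and B of 10.6, and 13.2:

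1. State in 10.6 A that every PAAE, whatever its seriousness, relatedness or expectedness, is entered on the AE page through the hospital stay, with those three attributes as fields.
2. State there that every SAE judged related, or leading to discontinuation of study drug, is entered regardless of expectedness.
3. Keep the two-part filter only as the trigger for expedited reporting (the 72-hour submission and DSMB review).
4. Word the SIRB sentence in 13.2 so that it matches what is recorded.
5. Add to 11.4.4 a table of PAAEs by arm and seriousness.

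The cost is protocol wording and a few extra AE entries per site. Because the additions are limited to PAAEs (four types are listed in 13.5) and to related or discontinuation-causing SAEs, sites are not asked to log routine complications of sepsis.

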The site investigator, study coordinator, or designee is responsible for entering all AEs and SAEs and updating the information (e.g., date of resolution, action taken) in a timely manner. SAEs meeting criteria should be submitted within 72 hours.

AE, PAAE and SAE reports will include, but are not limited to: the adverse event term, subject identifier, description of the event, concomitant medication used to treat the adverse event, Investigator assessment of causal relationship to the Investigational Product and/or research participation and any other relevant information.

ii. Reporting of SAEs to the DCC:

The Investigator or designee will complete an electronic SAE Report Form, assess the causal relationship to study procedure/intervention, and enter the information in the EDC system. This initial report should describe whether the SAE has resolved or is continuing, if and how it was treated, and whether the subject continued or permanently discontinued study participation.

The DCC will review all site submitted SAEs to determine if the event is indeed an SAE. In some cases, submitted SAEs may be downgraded to a PAAE. Such PAAEs will not be forwarded to the Medical Monitor or CCC, but instead be reviewed in aggregate along with other PAAEs at quarterly intervals for DSMB review and summarized and reported for the annual IRB continual renewal.

[figure not shown]
The DCC will then contact the Medical Monitor at the CCC for review of the electronic SAE Report Form and the supporting source documents. The CCC will report to the DSMB chair for review per the DSMB charter. If an ongoing SAE significantly worsens in its intensity or the relationship to study drug changes significantly, follow-up information will be provided by the site Investigator or designee within 72 hours of knowledge of this new information using the same procedure as described for transmitting the initial report. Based on reports delivered to the DCC, the CCC will report SAEs following SIRB criteria.

iii. Reporting to the IRB:

All PAAEs and SAEs will be reported as described above to the JHU SIRB in accordance with SIRB reporting requirements and may be reported locally, as determined to be required by each relying site.

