13.4. Data Safety Monitoring Board (DSMB)

Data and safety monitoring will be carried out by a designed Data Safety and Monitoring Board (DSMB) to ensure and maintain the scientific integrity and ethical balance of human subjects' research, and to protect subjects from avoidable harm. Data review by the DSMB throughout the trial will assure that the trial can continue without exposing participants to avoidable or unreasonable risks or harm.

The VICTAS Trial Data and Safety Monitoring Board (DSMB) will be composed of 5 individuals (2 emergency medicine clinicians, 2 critical care clinicians and 1 statistician) with specific content expertise in sepsis, multicenter clinical trials, and adaptive trial design and implementation. The DSMB will meet at least twice a year until study completion. The DSMB will report and advise the VICTAS Executive Committee. The DSMB is charged with ensuring that the trial is implemented as designed, that the prespecified design continues to be scientifically and ethically appropriate, and with reviewing ongoing safety data at the designated time points during the trial. The DSMB's obligation is to the continuing safety of trial subjects and those yet to be recruited to the trial, as well as the continuing validity and scientific merit of the trial in accordance with federal guidelines. (http://www.fda.gov/downloads/RegulatoryInformation/Guidances/ucm127073.pdf)

Acting independently of the Marcus Foundation, without interest in influencing the outcome of the study, DSMB member responsibilities include:

- protecting the safety of the study participants from avoidable harm;
- reviewing the charter, the research protocol and plans for data and safety monitoring and the informed consent template;
- evaluating the progress of the trial, including periodic assessments of data quality and timeliness, recruitment, accrual and retention, participant risk versus benefit, performance of the trial sites and study, and other factors that can affect study safety and outcome;
- reviewing interim analyses for safety issues and making recommendations in accordance with pre-specified safety stopping rules agreed upon by the Executive Committee and the DSMB;
- making recommendations to the Executive committee chairs concerning continuation, termination or other modifications of the trial based on the observed beneficial or adverse effects of the treatment under study;

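### Section 10.6 lets the data coordinating center reclassify a site-reported SAE as a PAAE without stated criteria, and the reclassified case bypasses the Medical Monitor

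*Combined protocol and SAP*

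**What the plan says.** Section 10.6, part B.ii, sets the path of an SAE once a site has entered it:

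- The first reviewer is the DCC: "The DCC will review all site submitted SAEs to determine if the event is indeed an SAE".
- Reclassification is allowed: "In some cases, submitted SAEs may be downgraded to a PAAE".
- A reclassified case takes a separate path: "Such PAAEs will not be forwarded to the Medical Monitor or CCC, but instead be reviewed in aggregate". That aggregate goes to the DSMB every quarter and into the yearly IRB renewal.
- A case that is not reclassified goes to a physician: "The DCC will then contact the Medical Monitor at the CCC for review of the electronic SAE Report Form and the supporting source documents". The clinical coordinating center (CCC) then reports to the DSMB chair.

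Part A of the reporting rules in the same section limits the SAEs that sites submit to those that are "unexpected and deemed to be study related". For PAAEs it adds: "PAAEs deemed to be serious will be reported as per the SAE reporting process below". The definitions earlier in Section 10.6 promise expedited DSMB reporting of serious, unexpected events judged definitely or possibly related to the study.

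**The concern.** The decision that an event is not serious is made before the plan's medical reviewer has seen the case, and it is also what keeps the case from that reviewer. Section 10.6 does not say who at the DCC decides, on what grounds, or whether the investigator must agree. Section 12 describes the DCC's work mainly as data management, and its medical staffing is not described anywhere.

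Few events enter this path. Sites send in SAEs they consider unexpected and study related, together with serious PAAEs, which are by definition events linked to known risks of the study drugs. These are the reports most likely to carry a safety signal. A wrong downgrade replaces individual medical review with a line in an aggregate while other subjects continue to be randomized and dosed.

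**Working it through.** The point rests on wording. No sample size, power or alpha figure is involved, and the plan states no figure to reproduce.

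**1. The two routes side by side (Section 10.6, part B.ii)**

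| Step | SAE upheld by the DCC | SAE downgraded by the DCC |
|---|---|---|
| Site submission | within 72 hours | within 72 hours |
| Medical Monitor | reviews report form and source documents | does not receive it |
| CCC | receives it, reports to DSMB chair | does not receive it |
| DSMB | individual case via the chair | quarterly aggregate |
| IRB | CCC reports under the single IRB's criteria | summary at annual renewal |

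Both routes share the 72-hour limit, which applies to the site. No deadline is given for the step from DCC to Medical Monitor. What can be compared is therefore individual against aggregate review, not 72 hours against three months.

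**2. Does the rule for serious PAAEs close the gap?** Part A says: "PAAEs deemed to be serious will be reported as per the SAE reporting process below". That process is the one in part B.ii, which contains the downgrade step. A serious PAAE enters it, the DCC judges whether it is an SAE, and a negative judgment returns it to the aggregate. The rule protects an event that the DCC agrees is serious. It does not protect one that the DCC has misjudged.

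**3. Is the reclassification well defined?** Sections 10.6 and 13.5 define a PAAE by type of event (for example nephrolithiasis or hemolysis). Section 10.6 defines an SAE by seriousness. An event can be both, as part A recognizes. The two terms are not grades of one scale, so moving a case down from SAE to PAAE has no fixed meaning.

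**4. Do other sections restore individual review?**

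- Section 8.5 (Treatment Compliance and Discontinuation) has the site investigator tell the DCC of possible reactions. Onward reports to the CCC are prepared only as needed, so the DCC again decides.
- Section 13.2 sends serious events to the single IRB whatever their cause. Under Section 10.6 the CCC makes those SAE reports, and downgraded cases are not forwarded to it. Section 13.2 is also broader than part A, which limits site submission to unexpected, related SAEs.
- Section 13.4 provides a DSMB with four clinicians, but Section 10.6 gives it these cases in aggregate.

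**5. Size of the possible wait**

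Inputs: 500 subjects in about 36 months (Section 6.4); 1:1 allocation (Section 11.2); quarterly aggregate (Section 10.6).

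- Accrual per month: 500 / 36 = 13.9
- Randomized in a full quarter: 3 × 500 / 36 = 41.7, about 42
- Of these on active drug: 41.7 / 2 = 20.8, about 21

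This is the longest wait, for an event arriving just after a quarterly report. Section 13.4 says: "The DSMB will meet at least twice a year until study completion". If the quarterly report were read only at meetings held at that minimum, the count would be 6 × 500 / 36 = 83.3, about 83 (about 42 active). That is an assumption, because Section 10.6 specifies quarterly review, so the conclusion does not rest on it.

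**The case against.** The strongest reply is that the DCC's test is seriousness. Read with the rule for serious PAAEs, the plan intends to downgrade only events that are not serious, and a serious reaction waits only if the DCC makes a mistake. That is right, and it limits the point to an error with no stated safeguard. A reader might infer more, that hemolysis or hypersensitivity leaves the SAE route merely because it is a listed PAAE. No sentence says so.

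Other stronger readings also fail:

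- A reader might infer that an unlisted event cannot be a PAAE. Section 10.6 makes the list open-ended.
- A reader might infer that all seriousness calls need medical judgment under the definition. That wording qualifies only the sixth criterion.
- A reader might infer that no physician is involved at all. The site investigator assesses causality, may stop study drug and follows the event, and the DSMB includes clinicians. What is missing is individual medical review of the downgrade.
- A reader might infer that downgraded cases drop out of the SAE table. Section 11.4.4 promises complete listings and does not say whose rating fills that table, so this is possible but not established.
- A reader might size the wait from 20 sites (Section 6.4) at 2 subjects a month each (Section 9.2), or 40 a month. That would fill 500 places in 500 / 40 = 12.5 months, against the stated 36, so it is not used.

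The DCC also has safety tasks beyond data management (Sections 8.5, 13.5 and 13.8), so medical review inside it cannot be ruled out. The reporting diagrams are not shown, and the DSMB charter and Monitoring Plan are not supplied, so a safeguard there cannot be excluded either. One that sent these cases to the Medical Monitor would, however, contradict the protocol's categorical sentence.

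**Conclusion.** The point stands as a gap in the reporting path. As written, the DCC alone can turn a site-reported SAE into a PAAE on unstated grounds, and the protocol then bars that case from the Medical Monitor and the CCC. If the judgment is wrong, a serious, study-related event also misses expedited DSMB reporting and is next seen in a quarterly aggregate.

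The possible wait covers up to about 42 further randomizations, about 21 on active drug. This assumes even accrual at the planned rate, 1:1 allocation and a full quarter's delay. It does not estimate how many events would be misclassified, for which the documents give no basis. The routing itself is plain from the text. How far it would matter in practice depends on documents not available here. The point warrants a protocol change because a stated rule can be replaced by a safer one at little cost.

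**What to change.** In Section 10.6, part B.ii:

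1. Delete the sentence containing "Such PAAEs will not be forwarded to the Medical Monitor or CCC, but instead be reviewed in aggregate".
2. Send every site-submitted SAE to the existing Medical Monitor. The DCC may propose a reclassification, with its reason, and the Medical Monitor confirms or rejects it.
3. State the criteria for reclassification as a decision on seriousness, recorded separately from whether the event type is a PAAE.
4. Keep the investigator's seriousness rating in the database alongside any later one.

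In Section 11.4.4, state which rating the SAE table uses. Reconcile the expedited-reporting definition and reporting rules of Section 10.6 with Section 13.2, so that one rule says which serious events sites submit, who reclassifies them and who reports them to the single IRB.

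The cost is protocol wording and some extra case reviews by the Medical Monitor. No new role is needed. The number of extra reviews cannot be estimated from the documents.
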